1. TITLE

Urogynecological Office Visits and Patient Satisfaction of Limited English-Proficient patients with phone Interpreter Services compared to In-Person Interpreters: Randomized Controlled trial (SIP)¹

2. EXTERNAL IRB REVIEW HISTORY*

N/A

3. PRIOR APPROVALS:

None

Conflict of Interest (COI): N/A

Clinical Engineering Department: N/A

Biohazardous Agents: N/A

Radiation: N/A

4. OBJECTIVES*

Primary Objective: To determine if In-person interpreters increases patient satisfaction of Urogynecological(URGYN) office visits compared to the use of phone interpreter services for Limited English Proficient (LEP) patients

Secondary Objective: To determine if type of provider, years spent in the US, income level, or level of education influences patient satisfaction of UROGYN office visits

5. BACKGROUND*

Cultural and linguistic competence are two vital principles, regardless of specialty, providers and health care systems must understand to offer quality health care to patients. Linguistic competence, initially described in 2004 by Good and Jones refers to an organization and provider's capacity to respond effectively to the health literacy needs of the populations served¹. The National Center for Cultural Competence (NCCC) for years has emphasized the importance of cultural and linguistic competence as a fundamental aspect of quality health care and mental health care for diverse populations¹. Moreover, this awareness is key to develop essential strategies for reducing health care disparities by improving access, utilization and quality of care.¹

Both linguistic and cultural competency are important; however, in recent years there has been published literature investigating strategies to optimize linguistic competence. To improve upon current linguistic competence, the field of Emergency Medicine has studied and researched key ways to improve its linguistic competence, mainly by investigating the optimal way of providing translation services to patients. Barriers are created when the patient and physician do not speak the same language this can have a negative impact on patient satisfaction. It has been reported in the literature one way to limit this barrier is by using in-person interpreter for all limited English proficiency (LEP) patients. Bagachi et al randomized patient presenting to the ED to receive in person interpreter services or the usual interpreter services (Ad Hoc and telephone).² They concluded that use of in person interpreters significantly increased patients' and providers' satisfaction.² Garcia et al found similar results when they evaluated the influence of hospital

INVESTIGATOR STUDY PLAN

trained, Ad Hoc, and telephone interpreters on perceived satisfaction of limited English proficient parents presenting to a pediatric Emergency Department⁴. In their study, they found parents of patients were significantly more satisfied ($p <0.001$) with in person hospital trained interpreters.⁴ Patient satisfaction can impact a variety of outcome measures, one being, satisfied patients are more compliant with recommended treatment plans³ Patient satisfaction in the ED setting has also been associated with improved patient understanding of self-care and follow up plans, reduced errors, and better treatment adherence². It is for these reason providers and organization try to optimize patient satisfaction.

It is logical to assume that patients will have improved patient satisfaction with the use to in person interpreters in other specialty areas as well; however, to our knowledge this has not been evaluated or reported in the Urogynecology literature. In a rapidly evolving field that focuses primarily on quality of life outcomes, it is important we adequately communicate with our patients to offer appropriate treatment plans. In our study, we evaluated LEP patient's satisfaction of UROGYN office visits with phone interpreter services compared to in-person interpreters.

References

3. Boudreaux ED, O’Hea El. Patient Satisfaction in the emergency department: a review of the literature and implications for practice. *J Emerg Med*. 2004;26:13-26.
5. Gany et al. Patient Satisfaction with Different Interpreting Methods: A randomized Controlled Trial. *J Gen Intern Med* 2007. 22 (suppl 2): 312 -318.

6. INCLUSION AND EXCLUSION CRITERIA*

Inclusion Criteria:

INVESTIGATOR STUDY PLAN

- LEP speaking Spanish and Portuguese female patients presenting to the U Mass UROGYN clinic with or without Ad-hoc interpreters
- Spanish and Portuguese speaking female patients with LEP presenting to the U Mass UROGYN clinic for an office visit of any type

Exclusion Criteria:

- Unable to provide consent
- Under 18 years of age
- Pregnant women
- Prisoners
- LEP subjects who decline interpreter services
- Non -Spanish or Non – Portuguese speaking subjects
- Patients with cognitive impairment
- Visually or hearing impaired patients
- Patients not requiring a follow up appointment

7. STUDY-WIDE NUMBER OF SUBJECTS*

N/A

8. STUDY-WIDE RECRUITMENT METHODS*

N/A

9. STUDY TIMELINES*

Subjects will be enrolled and randomized at their initial visit and participation will occur at the subsequent visit. Participation will be for the duration of the single subsequent office visit, and then participation will be done.

Our Urogynecology department has approximately 15 Spanish or Portuguese LEP per month and given this trend we anticipate approximately 14 months for recruitment of patient. Taking into consideration time needed for data entry, statistical analysis, and manuscript writing we anticipate the duration of the study will be 17 months.

10. STUDY ENDPOINTS*

The primary outcome, patient satisfaction will be measured by a fourteen-item questionnaire previously used and internally validated by Garcia et al. The questionnaire has 3 sections that evaluates satisfaction with the interpreter, provider, and nurse. We will be assessing the interpreter satisfaction section scores of each subcategory as well as the overall score. All items are answered on a scale of 1 to 4 and weighted on a 100 - point scale.

Secondary outcomes evaluate patient satisfaction in relation to type of provider, years spent in the US, income level, and level of education.

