12. DATA AND SPECIMEN BANKING*

N/A

13. Data Analysis and Management*

Power calculations were based off findings from Garcia et al. which showed a mean difference of 12 between telephone and translator nursing satisfaction scores. In their study patients' satisfaction was evaluated looking specifically looking at three main subcategories, nursing, physician, and interpreter satisfaction. Sample size calculations were based off seeing a minimum of 12-point difference between mean scores for nursing satisfaction. Our sample size is of sufficient enough size to detect a meaningful difference between mean scores of the other two subcategories as well. We calculated an initial sample size of 48 with a significance level of 5% and power of 80%. Taking into consideration data analysis with multivariate linear regression analysis we added 10 additional participants per variable (Expected dependent variables include: English fluency, interpreter service experience, language, and age)

INVESTIGATOR STUDY PLAN

48 +(10 x 4) = 88. Based on our patient population and taking into consideration potential conflicts that could arise with patients cancelling follow up appointments we are expecting a 30% drop out rate. This gave us to a final total sample size of 114 (57 each arm)

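### Section 10 places two to four satisfaction scores under one primary outcome without saying which decides, and section 13 gives power only for the nursing score

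*Combined protocol and SAP*

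**What the plan says.** The primary objective in section 4 is singular and names no score: "To determine if In-person interpreters increases patient satisfaction of Urogynecological(URGYN) office visits compared to the use of phone interpreter services".

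Section 10 makes patient satisfaction the primary outcome, measured by a fourteen-item questionnaire scored to 100 points. It adds: "The questionnaire has 3 sections that evaluates satisfaction with the interpreter, provider, and nurse". The next sentence is "We will be assessing the interpreter satisfaction section scores of each subcategory as well as the overall score". The secondary outcomes that follow relate satisfaction to provider type, years in the US, income and education. None of the section scores is listed among them, so all the scores stand under the primary outcome.

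Section 13 contains the only power calculation: "Sample size calculations were based off seeing a minimum of 12-point difference between mean scores for nursing satisfaction" and "We calculated an initial sample size of 48 with a significance level of 5% and power of 80" per cent. On the remaining sections it says: "Our sample size is of sufficient enough size to detect a meaningful difference between mean scores of the other two subcategories as well". The overall score does not appear in section 13.

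**The concern.** The sentence on scores in section 10 has two natural readings. In one, the interpreter section and the overall score are assessed (two scores). In the other, all three sections and the overall score are assessed (four scores). Under either reading, no passage ranks the scores, says which one answers the section 4 objective, or says how the single 5% level is used if more than one is tested.

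Two things are at stake.

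- **Selection.** The deciding score could be chosen after the data are seen. If the scores disagree, for example the interpreter score is positive and the overall score null, the plan gives no answer to its own primary question.
- **Meaning of the stated power.** The 80% belongs to a score that is never declared primary. Under the two-score reading, the nursing score is not even among the section scores to be assessed. A null result on the overall or interpreter score therefore cannot be read against the 80%.

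**Working it through.** **1. The plan's own figure.** Inputs from section 13: difference 12 points, significance 5%, power 80%, initial size 48. The 48 is a total, because 48 + 40 = 88, 88 × 1.30 = 114.4, and 114 is split as 57 per arm. That leaves 24 per arm. No SD is given, so 48 cannot be reproduced directly; it can only be solved backwards. With a two-sided t-test (an assumption, since sidedness is not stated), 24 per arm at 80% power gives a standardised difference of 0.826. The implied nursing SD is 12 / 0.826 = 14.5. The normal approximation gives 14.8. No equivalent calculation can be made for the interpreter, provider or overall score, because the document gives neither a difference nor an SD for them.

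**2. Error rate if any significant score counted.** The plan does not state this rule; it is used only to size the consequence. Let Z1, Z2, Z3 be the null test statistics of the three sections, with common correlation ρ. Take the overall score as their equally weighted sum (an assumption):

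Z0 = (Z1 + Z2 + Z3) / √(3 + 6ρ)

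The correlation of a section with the overall score is then √((1 + 2ρ)/3), which is 0.73 at ρ = 0.3 and 0.97 at ρ = 0.9. Each score is called significant if |Z| > 1.96. Results from 2,000,000 simulated draws per correlation:

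| ρ | Two scores, either direction | Four scores, either direction | Two scores, favouring in-person | Four scores, favouring in-person |
|---|---|---|---|---|
| 0.3 | 8.2% | 14.4% | 4.1% | 7.2% |
| 0.5 | 7.7% | 12.9% | 3.8% | 6.5% |
| 0.7 | 7.1% | 11.0% | 3.5% | 5.5% |
| 0.9 | 6.2% | 8.3% | 3.1% | 4.2% |

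The reference values for a single score are 5% in either direction and 2.5% in one direction.

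**3. Sensitivity to section weights.** The document does not say how the fourteen items divide among the sections. Letting the interpreter section hold 2 to 8 items, with the rest split about equally, and letting ρ run from 0.9 to 0, gives 5.8% to 9.6% for two scores and 8.3% to 16.0% for four, in either direction. With equal weights and ρ = 0 the values are 8.8% and 16.1%. The 8.8% is therefore not an upper limit, since unequal weights reach 9.6%.

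**4. Rules under which nothing is inflated.** If one prespecified score decides, the rate is 5%. If all scores must be significant, it is at most 5%.

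**The case against.** The best defence is that section 10 speaks of one outcome measured by the questionnaire as a whole. That points to the overall score, with the sections as components. On that reading the fault is an unclear sentence and not an uncontrolled multiple-endpoint design. This has force, and the overall score is the most natural candidate. But the plan does not say so, and section 13 is built on a different score.

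A second defence is that section 13 may have sized the trial on its most demanding section, which would explain why the size is said to serve the other two. The support may lie in the cited study, which is not available here. The fair statement is that this document gives no difference or SD for those sections. Even on this reading, the overall score is not covered.

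Three stronger readings are tempting but not supported:

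- *That the trial's false-positive rate is 6–14%.* This needs the rule that any significant score counts, and the plan does not adopt it.
- *That 6–14% is the error of concluding that in-person interpreters increase satisfaction.* That claim has a direction. Its rates are the last two columns of the table: for two scores they stay below 5%, and for four they exceed 5% only at the lower correlations. The proper comparison is 2.5%, so inflation remains, but it is smaller in absolute terms.
- *That the trial is underpowered for its primary outcome.* The document gives no SD for any score, so a shortfall cannot be shown.

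**Conclusion.** The point holds in a limited form. Two to four scores stand under one primary outcome, none is named as deciding, and the only stated 5% and 80% belong to the nursing score. The plan as written leaves the deciding score open until after the data are seen, so this is more than a missing detail and should be fixed.

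Its size is conditional. If any significant score counted, the chance of a false difference would be about 6–8% (two scores) or 8–14% (four). The chance of a false result favouring in-person interpreters would be about 3.1–4.1% or 4.2–7.2%. These figures assume two-sided 5% tests, equal section weights and between-section correlations of 0.9 to 0.3.

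**What to change.** **Section 10.** Name one primary score, compared between arms at a two-sided 5% level, and call the remaining scores secondary, reported with confidence intervals. The overall score fits the section 4 objective; the interpreter section is also defensible. The choice is the sponsor's. Suitable wording, if the overall score is chosen: *The primary outcome is the overall satisfaction score on the 100-point scale, compared between arms at a two-sided 5% level. The interpreter, provider and nurse section scores are secondary.*

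**Section 13.** Restate the power or detectable difference for the named score at the expected evaluable number, giving its SD, the sidedness and the analysis model (the section plans a regression). The plan's figures allow 88 evaluable, or 114 × 0.70 = 79.8, about 80. Which applies depends on how the 30% dropout allowance is meant, a separate matter. Either support the sentence on the other two sections with their expected differences and SDs, or delete it.

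**Cost.** Wording only, with no extra patients or data. The scores not chosen lose confirmatory status. If the overall score is chosen and the effect is confined to one section, the effect is diluted: 12 points in one section become 12 / 3 = 4 points on an equally weighted overall score.

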11. PROCEDURES INVOLVED*

This study is a randomized controlled trial. Patients presenting to our UROGYN clinic will be screened for eligibility using inclusion and exclusion criteria.. LEP patients will be identified as patients that

INVESTIGATOR STUDY PLAN

initiate conversation in a non-English language and are only able to communicate adequately regarding their medical problem in a non-English language. This definition was adapted from a previously used technique to identify LEP patients as described by Gany et al.⁵

After patients, have been seen for their scheduled office visit they will be invited to participate in the study. Once the patient has agreed to participate in the study the participant will be randomized. Participants will be given ample time to read the fact sheet and given the opportunity to take the fact sheet home for further review if they choose. Participants must call to be enrolled prior to their next visit, because randomization will occur before the follow up visits. No randomization will occur at the follow-up visit. Patients cannot request to be enrolled at the time of the follow up visit. Study assignment will be revealed using sequentially numbered sealed opaque envelopes. Randomization will be performed using software and a block randomization scheme to yield a 50% chance of having an in-person interpreter.

Portuguese and Spanish LEP participants will be randomized from two separate blocks. Bilingual participants will be identified at that time and be asked the primary language they would like for medical interpreter services for the subsequent office visit. Those assigned to the control group will receive phone translation services and the experimental group will have in person interpreters. Once randomized, research team members will make a note in the computer scheduling system if an in-person interpreter is needed for the next visit.. At the subsequent visit, demographic information will be collected and patients will then receive interpretation services from the phone or an in-person interpreter.

At completion of the follow up visit subjects will complete two forms, in their native language. The first form is a fourteen-item patient satisfaction questionnaire that has been previously used in published studies. The first form also has two questions from the Consumer Assessment of Healthcare Providers and System Hospital Survey (www.cahps.ahrq.gov). The second form will assess subjects English proficiency, overall health status, and yearly household income.

For eligible patients who decline participation we will be collecting non-identifiable information including; patient age, type of visit, language, provider, and if the patient was alone for the visit. This will provide us non-identifiable data for comparative analysis between the group of eligible patients who agreed to participate and those who declined.

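### Patient-reported covariates are collected only at the outcome visit, so they will be missing for the roughly 30% expected not to return, and English fluency is measured after exposure to the assigned interpreter mode

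*Combined protocol and SAP*

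**What the plan says.** Section 11 (Procedures Involved) sets the order of events. Allocation comes first: "Participants must call to be enrolled prior to their next visit, because randomization will occur before the follow up visits". Language is known at that point, because Spanish and Portuguese speakers are randomised from separate blocks, and bilingual patients are asked which language they prefer. The other patient characteristics wait for the return visit: "At the subsequent visit, demographic information will be collected and patients will then receive interpretation services from the phone or an in-person interpreter". The forms come last: "At completion of the follow up visit subjects will complete two forms, in their native language". Of these, "The second form will assess subjects English proficiency, overall health status, and yearly household income".

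Section 10 (Study Endpoints) shows what the items are for: "Secondary outcomes evaluate patient satisfaction in relation to type of provider, years spent in the US, income level, and level of education". Section 13 (Data Analysis and Management) names English fluency, interpreter service experience, language and age as the regression variables. It also gives the cause and size of the expected loss: "potential conflicts that could arise with patients cancelling follow up appointments we are expecting a 30% drop out rate". Section 15 keeps patients who miss the follow-up visit in the study.

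For eligible patients who decline, section 11 says "we will be collecting non-identifiable information including; patient age, type of visit, language, provider, and if the patient was alone for the visit", so that they can be compared with those who agreed. No similar comparison of attenders with non-attenders is described, and section 13 has no missing-data or attrition analysis.

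**The concern.** The expected loss falls between randomisation and the only visit at which patient-reported characteristics are recorded. The patients whose absence could disturb the randomised comparison are therefore those about whom least is known. If the kind of patient who fails to return differs between the arms, the arms compared at follow-up are no longer the arms that were randomised. The data that might show this, or support a correction, would not exist.

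A second problem arises even with full attendance. A patient knows whether her interpreter was in the room or on the telephone. She rates her English only after that experience, and the answer is then meant to serve as an adjustment variable for the treatment comparison.

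**Working it through.** **1. The plan's sample size.** Section 13 gives 48 + (10 x 4) = 88. Then 88 x 1.30 = 114.4, which reproduces the stated 114 (57 per arm).

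**2. Expected loss at the stated rate.**
- Total: 114 x 0.30 = 34.2, about 34 patients.
- Per arm, if equal: 57 x 0.30 = 17.1, about 17 patients.
- Remaining: 114 x 0.70 = 79.8, about 80 patients. This is below the 88 sought, because 88 was multiplied by 1.30 and not divided by 0.70 (88 / 0.70 = 125.7). That is a separate point.

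**3. What is known about a randomised patient who does not return.**

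| Item | Use in the plan | When obtained | Known for a non-returner? |
|---|---|---|---|
| Assigned arm | Primary comparison | Randomisation | Yes |
| Language | Block; regression variable | Randomisation | Yes |
| Bilingual status, preferred language | Choice of interpreter | Randomisation | Yes |
| Age | Regression variable | Clinic record (section 27 permits review) or comparison with decliners | Possibly; not committed to |
| Provider type | Secondary factor | As for age | Possibly; not committed to |
| Visit type | Comparison with decliners | As for age | Possibly; not committed to |
| Education, years in the US | Secondary factors | No point stated other than demographics at follow-up | No |
| Household income | Secondary factor | Form at end of follow-up visit | No |
| English proficiency | Regression variable | Form at end of follow-up visit | No |
| Interpreter experience | Regression variable | No point stated | No, as far as stated |
| Health status | No stated analysis | Form at end of follow-up visit | No |

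Three of the four secondary factors and two of the four regression variables would be missing for all of the roughly 34 patients lost.

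**4. What can still be done about attrition.** Arm is known for all 114, so losses can be counted over 57 and 57. Two assumed splits of 34 losses, tested with Fisher's exact test:
- 12/57 against 22/57: p = 0.06.
- 10/57 against 24/57: p = 0.007.

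A marked imbalance in numbers could thus be seen. An imbalance in who was lost, by education, income, years in the US or English fluency, could not. Equal counts do not exclude it.

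**5. Timing of English fluency.** The order is randomisation, visit with the assigned mode, then the form on which the patient rates her English. If the mode affects that rating, the covariate is partly a result of treatment, and conditioning on it can shift the estimated treatment effect in either direction. The documents give no figure from which the shift could be sized.

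**The case against.** Three stronger readings are tempting, and the documents support none of them.

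- *A reader might infer that attrition by arm cannot be examined.* It can. Arm is known for everyone randomised, and section 15 does not withdraw patients who miss the visit.
- *A reader might infer that the plan holds nothing on non-returners.* It holds language and bilingual preference. The planned comparison of those who agreed with those who declined also implies that age, visit type, provider and whether the patient was alone are recorded for all who agreed. Section 27 permits chart review, and section 26 keeps the link to the medical record until publication. No section commits to extracting these items for non-returners, but a partial look at attrition bias is possible.
- *A reader might infer that attenders in the two arms cannot be shown to be comparable.* They can be tabulated by arm, since they are the patients who supply the data. Section 11 also places demographics before the interpreted part of the visit, and education or years in the US are unlikely to change on learning the assignment. Post-exposure reporting is a concern only for the end-of-visit form.

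Two further arguments carry weight. First, the outcome is satisfaction with the follow-up visit, so a patient who never attends has no visit to rate; any missing-outcome analysis must say what it estimates. Second, earlier collection is not free: some patients take the fact sheet home and call to enrol, and section 16 treats income as optional and potentially embarrassing.

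These arguments narrow the point. They do not supply the missing patient-reported items, and they do not move English fluency ahead of exposure.

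**Conclusion.** The point holds in a limited form. About 34 of 114 randomised patients would have no data on education, years in the US, income, English proficiency or, as far as stated, interpreter experience. Attrition bias on those factors cannot be assessed or used in weighting or sensitivity analysis, and no attrition analysis is planned. Separately, a named regression covariate is self-reported after an intervention that patients necessarily recognise.

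The figure of 34 rests on the plan's 30%; the split of about 17 per arm assumes equal loss. It also assumes that education and years in the US belong to the demographics taken at follow-up, since no other collection point is given, and that interpreter experience is not recorded earlier. The size and direction of any resulting bias cannot be derived from the documents. This is an inexpensive improvement that should be made; it does not show that the primary comparison is invalid.

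**What to change.** 1. In section 11, collect the following after agreement and before the envelope is opened: the demographic items (naming education, years in the US and prior interpreter experience), English proficiency, health status and the income item, still optional. Ask them by telephone, with interpretation, for patients who call to enrol.
2. Keep only the satisfaction questionnaire and the two CAHPS items at follow-up. Align section 9, which places participation at the follow-up visit, and the fact sheet.
3. In section 13, report attrition by arm, tabulate the enrolment items by arm for attenders and non-attenders, and use the pre-randomisation values as the regression covariates.
4. Add a sensitivity analysis of the primary comparison, for example inverse-probability-of-attendance weighting. State its target (satisfaction had all randomised patients attended) and its assumption (attendance explained by the recorded items). With about 34 non-attenders, keep the weighting model small and specify it in advance.

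The cost is a minor protocol amendment, a few extra minutes or a telephone interview at enrolment, and forms completed for some patients who never return. No new instrument or change in sample size is needed for this point.

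### English proficiency is scheduled to be recorded only after the interpreted visit, so it should adjust the arm comparison only if it is asked earlier (minor, inexpensive to correct)

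*Combined protocol and SAP*

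**What the plan says.** The order of events is set out in sections 9 and 11 of the combined protocol and SAP.

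- **Randomisation comes first.** Section 9: "Subjects will be enrolled and randomized at their initial visit and participation will occur at the subsequent visit". Section 11 adds: "No randomization will occur at the follow-up visit".
- **Demographics are collected next, then interpretation.** Section 11: "At the subsequent visit, demographic information will be collected and patients will then receive interpretation services from the phone or an in-person interpreter". English proficiency is not named at this step.
- **The forms come last.** Section 11: "At completion of the follow up visit subjects will complete two forms, in their native language". On the content of the second: "The second form will assess subjects English proficiency, overall health status, and yearly household income". The items themselves are not shown.
- **Earlier language information is coarse.** The screen for limited English proficiency (LEP) is a yes/no judgement that the patient is "only able to communicate adequately regarding their medical problem in a non-English language". Around enrolment, "Bilingual participants will be identified at that time and be asked the primary language they would like for medical interpreter services". Allocation is separated by language: "Portuguese and Spanish LEP participants will be randomized from two separate blocks". None of these grades a patient's English.

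Section 13 names four variables for a multivariate linear regression (English fluency, interpreter service experience, language and age) and adds 10 participants for each. It calls them dependent variables, but since satisfaction is the outcome they can only sensibly be covariates. It does not write out a model or say whether the regression estimates the arm effect.

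**The concern.** Randomisation protects an arm comparison adjusted for characteristics fixed before the intervention. It does not protect one adjusted for something recorded afterwards that the intervention might have influenced. Here the patient knows which mode of interpretation she had, and answers about her English just after using it. An encounter that went smoothly, or one in which she struggled, could colour that answer. If the colouring differs by arm and the answer is related to satisfaction, adjusting for it moves the estimated arm effect, in a direction that cannot be known beforehand.

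Two inferences are needed before this bites. The first is that English fluency in section 13 is the English proficiency of section 11; no text equates them, but no other scheduled measure could supply it. The second is that the regression adjusts the arm comparison. That is the natural reading: the four variables stand in the sample-size paragraph for the arm difference, and none of them is among the secondary factors in section 10 (type of provider, years in the US, income, education).

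**Working it through.** **1. The plan's own figure.** Section 13: 48 + (10 × 4) = 88, and 88 × 1.30 = 114.4, which reproduces 114. English fluency accounts for 10 of the 40 added participants. With 30% loss from 114, about 80 are analysed (114 × 0.70 = 79.8); on the sponsor's arithmetic it is 88. I use 40 and 44 per arm.

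**2. Implied SD.** Section 13 gives a 12-point difference in nursing satisfaction, 5% significance, 80% power and 48 participants, but no SD and no statement of sidedness. For a two-sided two-sample t-test with 24 per arm, the detectable standardised difference is 0.826, so SD = 12 / 0.826 = 14.53. The normal approximation gives 14.8. If the test is one-sided, the normal approximation gives about 16.7.

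**3. Bias model.** Let U be true English proficiency in SD units, r its correlation with satisfaction within arm, and s the shift in the reported answer caused by arm, also in SD units.

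- Reported answer: M = U + s × arm
- Satisfaction: Y = 12 × arm + r × 14.53 × U + error
- Regressing Y on arm and M gives an arm coefficient of 12 − s × r × 14.53

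Both s and r are assumptions; the documents give neither. The signs are unknown, so the table shows absolute movement.

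| Shift s | r = 0.1 | r = 0.4 |
|---|---|---|
| 0 | 0 | 0 |
| 0.1 | 0.1 × 0.1 × 14.53 = 0.15 | 0.1 × 0.4 × 14.53 = 0.58 |
| 0.3 | 0.3 × 0.1 × 14.53 = 0.44 | 0.3 × 0.4 × 14.53 = 1.74 |

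The 0.3 SD row is a deliberately high bound. Simulation of the same model agrees to within 0.04 points. With SD 16.7 the extreme cell becomes 0.3 × 0.4 × 16.7 = 2.0 points.

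**4. Against the target and the standard error.** 1.74 / 12 = 14.5% of the target. The right yardstick for an adjusted estimate is the adjusted standard error. At r = 0.4 the residual SD is 14.53 × √(1 − 0.16) = 13.3.

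- 40 per arm: 13.3 × √(2/40) = 2.98, and 1.74 / 2.98 = 0.58
- 44 per arm: 13.3 × √(2/44) = 2.84, and 1.74 / 2.84 = 0.61

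**5. Power at the extreme.** With 40 per arm and a true 12 points, unadjusted power is 95.4%. With bias towards zero (12 − 1.74 = 10.26 points, SD 13.3) it is about 92.5%.

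**6. Price of leaving the covariate out.** The loss is SE × (1 − √(1 − r²)), with unadjusted SE = 14.53 × √(2/40) = 3.25. At r = 0.1 this is 0.02 points; at r = 0.4 it is 0.27 points.

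**The case against.** The strongest reply is that nothing in the plan as written is shown to be wrong. English ability does not change in one office visit. The form's items are not shown, no evidence suggests that answers drift by arm, and section 13 never says the regression estimates the arm effect. On the figures above, even an unsupported shift barely alters power.

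Most of that stands, and it is why the point is minor. What survives is the timing. The only scheduled measure comes after an unblinded intervention, and no text says it is to be treated as baseline or as unaffected by arm. The stability of the trait limits the likely bias but does not protect the answer given. Once the trial has run, a post-visit answer cannot be made into a baseline one.

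A reader might go further and infer that the trial's main result will be biased. The documents do not support this: the adjusted model is not stated, the shift is hypothetical, and a comparison without this covariate is untouched. A reader might also infer that the whole second form belongs at enrolment. That does not follow either: health status and income are not among section 13's four variables, and section 9 confines participation to the follow-up visit. Nor can one argue that screening for LEP makes the bias small by narrowing the range of English. A narrower range lowers the correlation but enlarges the same absolute shift in SD units, so the product is roughly unchanged.

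**Conclusion.** The point holds as a minor, low-cost improvement. If the section 13 regression adjusts the arm comparison, it would condition on a self-completed measure taken after randomisation and after exposure to the assigned interpreter mode. The movement is 0 if reporting does not shift by arm, and about 1.7 points (roughly 0.6 of the adjusted standard error) at the assumed extreme, or about 2.0 points if the test behind the sample size is one-sided. The trial's conclusion would rarely change. This rests on fluency and proficiency being the same variable, on the natural but unstated reading of the regression, and on the assumed correlation and shift. Age and language do not raise the issue. Interpreter service experience does: it is undefined, has no scheduled time of measurement, and could equally be affected by the visit.

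**What to change.** **Section 11.** Ask the English-proficiency item together with the demographic information already collected at the follow-up visit, before interpretation begins. If practical, ask it at enrolment instead, before the envelope is opened; section 9, which places participation at the subsequent visit only, must then be amended to match. Health status and income can stay on the post-visit form.

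**Section 13.** State the model for the arm comparison. Say that English proficiency, and likewise interpreter service experience, enters it only if recorded before the interpreted visit, and is otherwise left out. Use one name for the English variable in both sections.

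**Cost.** A minor amendment; the planned 114 need not change. At the demographics step, an item that section 16 calls potentially embarrassing is asked just before the visit, with assignment possibly known. At enrolment, it is asked of some who will not return, and those who enrol by telephone need a call in Spanish or Portuguese. If the sponsor prefers to omit the covariate from the arm comparison, the loss is at most about 0.27 points of standard error on the assumptions above.
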